25.0 Process to Document Consent in Writing

25.1 *Consult “SOP: Written Documentation of Consent (HRP-091)” for recommended procedures, and describe whether and how consent of the subject will be documented in writing:*

Prior to beginning the survey, participants will electronically agree to participate in the study by checking a box after being presented with the full version of the ICF in Qualtrics.

25.2 *If the research presents no more than minimal risk of harm to subjects and involves no procedures for which written documentation of consent is normally required outside of the research context, you can request that the IRB waive the requirement to obtain written documentation of consent (e.g., consent to participate is indicated by pressing a button for an online questionnaire – after the consent information is presented and before the questionnaire begins):*

Consent to participate is indicated by pressing a button for an online questionnaire – after the consent information is presented and before the questionnaire begins.

25.3 If you will document consent in writing, attach a consent document with places for signatures. If you will obtain consent, but not document consent in writing, please attach the consent script or text. Review “CHECKLIST: Waiver of Written Documentation of Consent (HRP-411)” to ensure that you have provided sufficient information. You should use “TEMPLATE CONSENT DOCUMENT (HRP-502)” to create the consent document or script:

The study will obtain consent, but not document consent in writing. The consent script is attached.

26.0 Resources Available

26.1 Describe the resources available to conduct the research. For example, as appropriate:

- *Describe the PI’s availability to supervise the research.*
- *Justify the feasibility of recruiting the required number of suitable subjects within the agreed recruitment period. For example, how many potential subjects do you have access to? What percentage of those potential subjects do you need to recruit?*
- *Describe the time that you will devote to conducting and completing the research.*
- *Describe your facilities.*
- *Describe the availability of medical or psychological resources that subjects might need as a result of an anticipated or unanticipated consequence of participation in the research.*
- *Describe your process to ensure that all persons assisting with the research are adequately informed about the protocol, the research procedures, and their duties and functions (e.g., training plans, detailed study notebooks).*

The PI’s primary focus is overseeing research efforts and will devote sufficient time to supervise the study.

We have a history of successful recruitment of individuals in recovery from AUD. All participants will enroll on a voluntary basis and electronically sign an IRB-approved informed consent form prior to study participation. In addition, we have more than

sufficient numbers of participants in our current REDCap database to recruit an adequate number of participants for the current study.

Contact methods that were previously successful in previous studies will be used to recruit for this study. Participants will be allowed to answer the surveys at a time and location of their convenience in an attempt to minimize barriers to participation and increase retention and survey completion.

The PI's office and Virginia Tech facilities reside on the 3rd floor of the Fralin Biomedical Research Institute (FBRI) and consists of several laboratories for clinical research. Office space for the PI, co-investigators, project manager, post-doctoral associates, and graduate students is provided in the FBRI.

This is a minimal risk observational study. In the unlikely event of any medical emergencies, study representatives will call 911 regardless of whether it is related to the study. If a participant reports depression or suicidal thoughts to any study representative, the participant will be provided with information about relevant resources (i.e., suicide hotlines and/or call 911, if appropriate).

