6.0 Setting

6.1 *Describe the sites or locations where your research team will conduct the research. Consider each of the items listed below:*

- *Identify where your research team will identify and recruit potential subjects.*
- *Identify where the team will perform the research procedures.*
- *Describe the composition and involvement of any community advisory board(s).*
- *For research conducted in other locations, describe:*
 - *Site-specific regulations or customs affecting the research at those locations.*
 - *Local scientific and ethical review structure at those locations. Examples include work in other cultures or ethnic groups (within or outside of the U.S.) and work with churches. The HRPP will provide additional guidance for international research.*

Location of Recruitment:

Participants will be recruited from our REDCap data base. Previously screened participants who have agreed to be re-contacted for other studies and that meet for the current experiment will be contacted via email with an invitation to participate in the current study.

Location of study:

The entirety of data collection will be conducted online. All participants will enroll on a voluntary basis and electronically sign an IRB-approved consent form prior to study participation.

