authenticate their access to the two surveys of the study. They will not have to provide any PII during the surveys following the pre-screen. Throughout the remaining of the study, the only personal information linked to their ID will be their email which will be needed to send the survey links and process the payments. Data will be stored in Qualtrics and only authorized people will have access to the data in Qualtrics. If data need to be downloaded from Qualtrics, those data will be stored in password-protected folders and only the participant's ID will be included in the file. No other PII will be stored together with the participants' responses to the surveys.

9.5 Please select the identifiers you will obtain (whether directly from participants or from another source), including but not limited to:

	Name
	Geographical subdivisions smaller than a state, including street address, city, county, precinct, zip code, and equivalent geocodes (note, the initial three digits of a zip code are not considered identifiable)
	Elements of dates (except year) for dates directly related to an individual, including birth date, admission date, discharge date, date of death, and single year of age over 89 and all elements of dates (including year) indicative of such age (note, such ages and elements may be aggregated into a single category of age 90+)
	Phone numbers
	Fax numbers
	Electronic mail addresses (e-mail)
	Social Security numbers
	Medical record numbers
	Health plan beneficiary numbers
	Account numbers
	Certificate/license numbers
	Vehicle identifiers and serial numbers, including license plate numbers
	Device identifiers and serial numbers
	Web Universal Resource Locators (URLs)
	Internet protocol (IP) address numbers
	Biometric identifiers, including finger and voice prints (audio recording)
	Full face photographic images and any comparable images (including video recording)

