All screened participants are assigned study IDs that are thereafter associated with all collected data, whether paper or electronic. The electronic de-identified data is stored on the [name] shared server which is password protected. Non-electronic data that is collected is stored in participant specific binders identified only by study ID. These binders are stored in a locked file room inside a locked office within ARRC. . Study ID and identifiers (i.e., name, email, age, and demographics) will be available together electronically only in the pre-screener in Qualtrics, a widely used secure web-based application. Specifically, we will use Qualtrics to collect demographic and other screening criteria for eligibility for study enrollment. This service is password protected and has been approved by Virginia Tech IRB.

Personally identifiable information (PII) and Protected Health Information (PHI) is strongly guarded at all points in the study procedures.

All online data collection will be completed using the participant's ID, and will not require entering any PII.

As the survey is computerized, self-administered, and directly entered into the secure server, only authorized researchers will have access to assessment survey responses.

Study laptops will be password protected with an encrypted file system.

19.4 For multi-site studies, describe how data or specimens will be handled and secured for each site (e.g., central or disseminated data storage, data coordinating center):

NA

19.5 Describe the plan for data disposition following the conclusion of the study (e.g., long term maintenance of data, data destruction methods).

- *What information will be included in the long term storage of data or specimens?*
- *How long will the data or specimens be stored?*

- *Where and how data or specimens will be stored?*
- *Who will have access to the data or specimens during long term storage?*
- *Who is responsible for receipt or transmission of the data or specimens?*
- *How will data or specimens be shared or transported?*
- *When and how will personal identifiers be destroyed?*

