20.2 Describe steps that you will take to make subjects feel at ease with the research situation in terms of the questions being asked and the procedures being performed. "At ease" does not refer to physical discomfort, but the sense of intrusiveness a subject might experience in response to questions, examinations, and procedures (e.g., use of a same gender investigator to place sensors on the torso, a private changing area if clothing must be changed, sensitivity when discussing pregnancy testing with subjects, making it clear on surveys that participants can discontinue at any time, not asking questions about private or sensitive issues unless necessary for the research):

The survey will be completed online in a location with sufficient privacy chosen by the participant. Participants will be reminded before starting the online survey that they may stop participation at any time without penalty.

As an additional protection against the risk of loss of confidentiality, we will use only ID numbers and keep all data in password-protected databases.

20.3 Describe how you plan to access existing sources of information about the subjects (e.g., medical records, grades) and how you will protect participant privacy through the data security plan:

All data will be encrypted and stored in password-protected secure server at ARRC.

20.4 Describe any required reporting that might occur as a result of your research questions, study populations, and data collection methods. Examples for Virginia and Virginia Tech include:

- *Any suspicions (e.g., circumstantial, disclosed) of child abuse (physical, emotional, sexual) and neglect*
- *Sexual discrimination and/or sexual violence that involves a student*
- *Disclosure or signs of intention to harm oneself (i.e., suicidal ideation and/or plan)*
- *Disclosure or signs of desire to harm others (i.e., homicidal ideation and/or plan)*
- *Suspected abuse, neglect or exploitation of vulnerable adults (e.g., individuals with a disability, elderly persons)*

We will report any disclosure or signs of intention to harm oneself (i.e., suicidal ideation and/or plan). In the event of this disclosure study staff will follow ARRC's SOP related to suicidal ideation.

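### The stated responses to participant distress begin only once staff know of it, but the online self-administered sessions give staff no described way to know, and section 17.2 is answered NA

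*Combined protocol and SAP*

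**What the plan says.** Four parts of the combined protocol and SAP bear on this.

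- **Risk.** Section 17.1 names adverse emotional reactions to research tasks as a foreseeable risk. Section 17.2, on measures to minimize risk and monitor safety, is answered NA.
- **Response in section 26.1.** For psychological distress: "If a participant reports depression or suicidal thoughts to any study representative, the participant will be provided with information about relevant resources", with suicide hotlines and, where appropriate, a 911 call given as the content. For physical events: "In the unlikely event of any medical emergencies, study representatives will call 911 regardless of whether it is related to the study".
- **Response in section 20.4.** "We will report any disclosure or signs of intention to harm oneself (i.e., suicidal ideation and/or plan", and "In the event of this disclosure study staff will follow" a local procedure on suicidal ideation. That procedure is not among the documents.
- **Format.** Section 6.1: "The entirety of data collection will be conducted online". Section 19.3: "As the survey is computerized, self-administered, and directly entered into the secure server". Section 20.2: "The survey will be completed online in a location with sufficient privacy chosen by the participant". Section 26.1 adds that participants also choose the time.

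On contact details, section 9.5 leaves "Phone numbers" unticked but ticks name, sub-state geography, e-mail and IP address. Section 9.4 says that after the pre-screener only e-mail stays linked to the study ID. Section 24.1 puts the full consent at the start of each survey and says the form carries contact information.

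**The concern.** The active narrative asks heavy drinkers (AUDIT of 16 or more, section 12.2) to picture losing home and car and being parted from their family. None of the exclusion criteria concerns depression or suicidality. The protocol accepts that tasks may upset people, then leaves the mitigation item blank in substance. What remains is a pair of responses that presuppose someone on the study team has been told or has noticed. That suits a laboratory visit. In a survey taken alone, nobody from the team is there to be told. At stake is whether a distressed participant who simply closes the browser receives anything under the plan. This is a participant-safety point. It does not touch sample size, power or type I error.

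**Working it through.** No arithmetic decides this, so the sections are set side by side.

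1. **What starts each response?** In 26.1, resource information follows a report to a study representative. The 911 sentence has no stated trigger, but a representative can call only after learning of the event. In 20.4, the trigger is a disclosure or signs, which is wider than a report.

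2. **How could staff learn of an event during a session?**
   - Live contact: none is described in either session (6.1, 8.1, 8.2, 19.3, 20.2).
   - Survey content: section 8.3 lists craving, withdrawal, life-stress, stress-appraisal and other scales. None is described as measuring mood or suicidality.
   - Review of answers: no check of responses for warning signs is described, so the word signs in 20.4 has no stated means of detection.
   - Meetings: section 21.1 has safety discussed at weekly personnel meetings. That is oversight of the study and not a route for one person's event during a session.
   - The participant writes in: possible, using the contact details on the consent form (24.1). This is the only route the documents show.

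3. **What can staff do once they know?** They hold e-mail and can re-identify the person through the pre-screener, where ID and identifiers sit together (9.4). Geography and IP address are also ticked in 9.5. Stored geography need not match the place chosen for a session, and no procedure for locating a participant during a session is described.

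4. **Do 20.4 and 26.1 agree?** Section 20.4 has staff report and follow the local procedure, without saying to whom they report. Section 26.1 has the participant given resource information, with 911 where appropriate, and mentions neither reporting nor the procedure. Both can be carried out for the same person. Neither refers to the other.

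5. **Resulting cases.**
   - Distressed and contacts staff: a response is stated.
   - Distressed, does not contact staff and gives no sign that staff would see: no stated response starts.

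6. **How many are exposed?** Section 14.1 plans 160 consented at 70% retention: 160 × 0.70 = 112 completers, and 112 / 2 = 56 per group. So 56 planned completers receive the active narrative in Session 2.

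**The case against.** The strongest reply is proportionality. The study is declared minimal risk (4.2, 26.1), and the template in section 21 requires safety monitoring only above that level. Participants are reminded that they may stop at any time without penalty, and they can be withdrawn if a contraindication emerges (16.1). The local procedure, and the monitoring plan cited in 10.1 for incidental findings, may supply detail not visible here. All of this stands, and it limits the weight of the point. It does not answer how staff would learn of an event: as cited, the procedure begins only after a disclosure.

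A reader might also infer more than the documents support:

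- *That 20.4 and 26.1 contradict each other.* They answer different template questions, and both can be followed. What is missing is a cross-reference.
- *That staff cannot reach participants because no phone numbers are obtained.* E-mail is linked to the ID and other identifiers are held. Only locating someone during a session is left undescribed.
- *That no support information is ever shown.* The survey screens and consent script are not in the documents, so this cannot be known.
- *That the NA in 8.6 rules out a closing page.* That item concerns deception and says nothing about other closing material.

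**Conclusion.** The point holds as a gap between the stated responses and the online format. A risk is listed, its mitigation item is answered NA, and the remaining responses wait for information that the design gives staff no described means of obtaining, apart from the participant making contact. Anyone who does make contact is covered by a stated response. It would go too far to say that an affected participant gets no response in general, or that this follows from the difference between 20.4 and 26.1.

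The gap is present for up to 160 consented participants. It matters most in Session 2, when the narrative is presented. No rate of distress can be derived from the documents, so no number harmed is claimed. The conclusion assumes that the unseen survey pages, consent script and local procedure do not already provide unprompted resource information or a means of detection. If they do, only the protocol wording needs to change. The change is worth making before further enrolment, but it does not bear on the validity of the analysis.

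**What to change.** Unless pages outside these documents already do it, show every participant the resource information that 26.1 already names, without waiting for a report. Place it on the consent page that opens each survey and on the final page after all assessments, in both surveys and identically in both arms. The opening page reaches those who stop early; the closing page reaches those who finish.

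This placement also protects the outcomes. Section 4.1 compares measures across sessions within participants as well as between groups. A link on every Session 2 page alone would make the post-exposure context differ from baseline, even with matched arms. Identical opening and closing pages in both surveys avoid that.

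Replace the NA in 17.2 with what is done. Reconcile 17.2, 20.4 and 26.1 with one another and with the online format, including how a disclosure or emergency would become known to staff. What the clinical response should be is for the sponsor and IRB to set.

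The cost is one static page, a few lines of protocol and consent text to go through IRB amendment, and slightly more reading for participants.

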27.0 Multi-Site Research

Contact the HRPP for multi-site research (involving multiple institutions) and the details required for this section will be provided. Otherwise, indicate N/A.

NA
